6.5 Demographics and Baseline Characteristics

Descriptive statistics will be presented for all clinically relevant baseline demographic, medical history, and clinical characteristic variables.

6.6 Analysis of Study Endpoints

6.6.1 Primary Endpoint

The primary objective is to evaluate the performance of the Osia 2 system on an adaptive speech in noise test in Cohort 1.

6.6.1.1 Primary Analysis

A paired t-test of superiority for the adaptive speech in noise test, comparing the aided and unaided conditions at 3-months relative to the preoperative (Visit 1) unaided condition. The mathematical statement of this hypothesis test is written as:

$$H_0: \Delta On \geq \Delta Off$$

$$H_1: \Delta On < \Delta Off$$

where ΔOn is the mean change in the adaptive speech in noise test between the 3-month aided (On) condition and the preoperative (Visit 1) unaided condition, and ΔOff is the mean change in the adaptive speech in noise test between the 3-month unaided condition (Off) and the preoperative (Visit 1) unaided condition. Successful rejection of the null hypothesis indicates the aided performance of the Osia 2 system is superior to the unaided performance based on the adaptive speech in noise test.

The endpoint will be assessed in the ITT analysis cohort with complete data preoperatively and at 3 months.

Statistical Analysis Plan		Page 11 of 13
Sponsor Cochlear Americas	Study A post-market interventional cohort study evaluating the clinical efficacy of the Osia 2 system in the US Market	Version 3.0

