7.1.1 Design Rationale

This clinical investigation design ensures that the results obtained have clinical relevance, scientific validity and address the clinical investigation objectives. A within subject research design has been employed to utilize each subject as his or her own control as it accommodates the heterogeneity that characterizes hearing impaired populations.

Subjects seeking treatment with an Osia 2 bone conductive device may present clinically as being aided or unaided, therefore it is important to capture both listening conditions to ensure a representative sample. Since the Osia 2 Sound Processor cannot be utilized in a non- surgical wearing configuration, each subject will be fit with the Baha 5 Power device on a Baha Sound Arc according to the Cochlear Baha Fitting prescription. The Baha 5 Power device is most comparable from a sound processing perspective to the Osia 2 Sound Processor.

A test order randomization paradigm has been employed to minimize test order effects and demonstrate the unaided to aided benefits of bone conduction technology. Due to the physiology of a conductive or mixed conductive hearing loss, there are no carry-over effects associated with the use of an osseointegrated bone conduction intervention and therefore comparisons can be made.

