7.2.7 Randomization Procedures

Subjects who meet eligibility criteria for enrolment will be randomized to a test order for the 3-month interval prepared by the Sponsor. Subjects will be randomly assigned to one of two test order configurations using a ratio of 1:1.

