9.4 Sample Size Determination

The planned sample size of 20 will provide greater than 95% power under a conservatively assumed mean of 12 and standard deviation of 15. Calculations are based on a one-sided 0.025 alpha and include allowance for attrition of up to 20%.

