4.1 Randomization

Test order for the 3-month interval will be randomly assigned in a 1:1 allocation ratio, stratified by site. Test order will be either aided followed by unaided, or unaided followed by aided.

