4.3 Study Assessments

The statistical analyses for the primary objective will be based on the 3-month assessment compared to the pre-operative baseline assessment. Analyses for the secondary objective will be based on safety data collected at the time of treatment and for the duration of the study up to and including 6 months.

Statistical Analysis Plan		Page 8 of 13
Sponsor Cochlear Americas	Study A post-market interventional cohort study evaluating the clinical efficacy of the Osia 2 system in the US Market	Version 3.0

5 Sample Size Determination

The planned sample size of 20 will provide greater than 80% power under a conservatively assumed mean of 12 and standard deviation of 15. Calculations are based on a one-sided 0.025 alpha and include allowance for attrition of up to 20%.

The primary objective is to evaluate the performance of the Osia 2 system on an adaptive speech in noise test. A paired t-test of superiority for the adaptive speech in noise test, comparing the aided and unaided conditions at 3-months relative to the preoperative (Visit 1) unaided condition. The mathematical statement of this hypothesis test is written as:

$$H_0: \Delta On \geq \Delta Off$$

$$H_1: \Delta On < \Delta Off$$

where ΔOn is the mean change in the adaptive speech in noise test between the 3-month aided (On) condition and the preoperative (Visit 1) unaided condition, and ΔOff is the mean change in the adaptive speech in noise test between the 3-month unaided condition (Off) and the preoperative (Visit 1) unaided condition. Successful rejection of the null hypothesis indicates the aided performance of the Osia 2 system is superior to the unaided performance based on the adaptive speech in noise test.

The secondary objective is to evaluate the safety of the Osia 2 system in a group of adult newly implanted recipients. Descriptive statistics specifically counts and percentages of device or procedure related adverse events captured through 6 months post-surgery will be summarized.

6 Statistical Analyses

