6.1.3 Statistical Significance

Hypothesis testing will be performed at the one-sided 0.025 significance level.

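### The primary paired t-test and its imputation model leave out the randomized test order; adding an order term is a cheap, minor to moderate improvement

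*SAP*

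**What the plan says.** SAP 4.1: "Test order for the 3-month interval will be randomly assigned in a 1:1 allocation ratio, stratified by site". The two sequences are aided then unaided, and the reverse. Protocol 7.2.7: "Subjects who meet eligibility criteria for enrolment will be randomized to a test order for the 3-month interval prepared by the Sponsor". Protocol 7.1.1 gives the purpose: "A test order randomization paradigm has been employed to minimize test order effects".

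The primary analysis (SAP 6.6.1.1) is "A paired t-test of superiority for the adaptive speech in noise test, comparing the aided and unaided conditions at 3-months", each expressed relative to the preoperative unaided score. Protocol 9.6 has the same paired t-test. Neither contains a term for order or period. SAP 6.1.3 sets the level: "Hypothesis testing will be performed at the one-sided 0.025 significance level".

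For missing data, SAP 6.6.1.2 imputes the aided-minus-unaided difference from age, sex and the preoperative unaided score. Order is not a predictor.

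Protocol 9.6 adds sensitivity tests for a period and a crossover effect. The SAP contains neither.

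For sample size, SAP section 5 uses a "conservatively assumed mean of 12 and standard deviation of 15" and allows for up to 20% attrition. The protocol plans up to 20 subjects at up to 6 sites. No block size and no expected order effect are given.

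**The concern.** The 3-month comparison is a two-period crossover within one visit. Visit 5 is planned at 4 hours, so practice or fatigue between the first and second test is possible, and the sponsor randomizes order for that reason. If the second test is systematically better or worse, each subject's difference carries plus or minus that order effect.

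A paired t-test without order handles this in one of two ways. With equal numbers in each order, the effect cancels in the mean but stays in the standard deviation, so the standard error is larger than it need be. With unequal numbers, part of the effect also stays in the mean. Unequal numbers are quite possible with about 20/6 = 3.3 subjects per site stratum, attrition of up to 20%, and no replacement of withdrawn treated subjects.

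What is at stake is some precision, and how well the single reported estimate and confidence interval reflect the split that actually occurred.

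**Working it through.** **Inputs.** Mean 12, SD 15, one-sided 0.025, N = 20, attrition 20%, hence 20 × 0.8 = 16 evaluable (SAP section 5 and 6.1.3). The mean is treated as the size of the benefit; in the hypotheses lower scores are better. Assumption: the order effect p, defined as the second test minus the first, is 2, 3 or 5 units. The documents give no value.

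**1. What is tested.** The preoperative score cancels: (aided − pre) − (unaided − pre) = aided − unaided at 3 months. The primary test is therefore a one-sample t-test on that difference, D.

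**2. The plan's own figure.** The SAP says "The planned sample size of 20 will provide greater than 80% power". From the noncentral t with noncentrality 12/(15/√16) = 3.2 on 15 df, power is 84.8%; with all 20 subjects it is 92.4%. The SAP's figure is reproduced. (Separately, from the same inputs the protocol says "The planned sample size of 20 will provide greater than 95% power", which neither 16 nor 20 evaluable subjects gives. The two statements need reconciling, but that is not this point.)

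**3. Model with an order effect.** D = τ + p·s + error, with s = +1 or −1 by order.

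**4. Equal orders (8:8), residual SD 15.** The unadjusted standard error is inflated by √(1 + (p/15)² × 16/15). For p = 5: √(1 + 0.1111 × 1.0667) = 1.058. The order-adjusted test has 14 df and power 84.5% whatever p is.

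| p | SE inflation | Power without order | Power with order |
|---|---|---|---|
| 2 | 0.9% | 84.4% | 84.5% |
| 3 | 2.1% | 83.8% | 84.5% |
| 5 | 5.8% | 82.0% | 84.5% (84.6% simulated) |

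The loss is under 1 point at 2 to 3 units and about 2.6 points at 5 (82.0% against 84.6%, both simulated). At p = 5 the unadjusted one-sided error is 2.0% rather than 2.5%, which is conservative.

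**5. Unequal orders (10:6).** The shift is p × (10 − 6)/16 = 0.25p. That is 0.5 units at p = 2 (4.2% of 12) and 1.25 units at p = 5 (10.4% of 12). The simulated one-sided error, given this split, is:

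| p | Split favors aided | Split favors unaided |
|---|---|---|
| 2 | 3.2% | 1.8% |
| 5 | 4.1% | 0.9% |

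**6. Over the randomization.** Averaged over site-stratified allocation in blocks of 2 or 4 (an assumption), 3 or 6 sites, 0 to 4 subjects lost and p from 2 to 5, the overall one-sided error is 2.0% to 2.5%.

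**7. How often orders are unequal.** With 6 sites, blocks of 2 or 4 and 4 of 20 lost at random, the two orders differ at all in about 66% to 70% of trials, and by 4 or more in about 19% to 23%. With 3 sites and 2 lost, a difference of 4 or more occurs in 7% to 11%.

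**8. Can the protocol's period test stand in?** At 8:8 and p = 5 its noncentrality is 2 × 5/(15 × √(1/8 + 1/8)) = 1.33, giving 24% power. It would usually miss the effect, and it does not change the primary estimate.

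**9. Cost of the order term with no order effect.** The standard error of the intercept is (15/2) × √(1/n1 + 1/n2). At 8:8 this is 3.75, noncentrality 3.2, power 84.5% on 14 df against 84.8% on 15 df. At 10:6 it is 3.87, noncentrality 3.10, power about 82%.

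**The case against.** The strongest reply is that counterbalancing does its work by design. Randomizing order makes the paired mean unbiased over the randomization and keeps the test valid without a model term, and the protocol also plans period and crossover tests. This stands. A reader might infer that the primary result is biased in favor of the device, that its type I error is inflated, or that the order randomization is wasted. Step 6 contradicts the first two, and protocol 7.1.1 the third. The shift exists only given a realized split, and can go either way.

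Second, the size is speculative. The adaptive test in protocol 7.3.1.3.2 runs in 5-dB steps and uses four tracks per condition, so a 5-unit order effect within a visit would be a full step. At 2 units the order term gains almost nothing at 8:8. The planning SD of 15 may also already include order variance. If it does, unadjusted power at 8:8 is about 85% to 86%, and the order term could add 0.2 to 2.6 points for effects of 2 to 5 units. This also stands. Power falls below 80% at 8:8 only for much larger effects (about 78% at 7.5 units on top of SD 15), which nothing in the documents supports.

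Third, a reader might infer that order is drawn before surgery and then disturbed by dropout. Protocol 7.2.7 says who is randomized but does not clearly say when, and the schedule of events has no randomization row. The timing is unspecified, so no conclusion should rest on it.

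What remains is that the estimate and interval come from one realized split, any imbalance is known at analysis, and correcting for it is nearly free.

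**Conclusion.** The point holds as a minor to moderate improvement to the primary estimator. Test order is randomized but enters neither the primary test nor the imputation model, and the SAP drops the protocol's order-related sensitivity tests. The consequence is conditional on the realized split: lost precision when orders are equal, and a shift of unknown direction when they are not. The figures rest on an assumed order effect of 2 to 5 units, residual SD 15 and 16 evaluable subjects. A smaller true SD would make a given order effect matter more for precision: at SD 5 (an assumption) and p = 3, the standard error at 8:8 is inflated by 18% rather than 2.1%. The documents do not support a claim of overall bias, of inflated overall error, or of a threat to the SAP's stated power.

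**What to change.** - **SAP 6.6.1.1 and protocol 9.6:** regress the 3-month aided-minus-unaided difference on test order coded +1/−1. Test the intercept, which is the mean of the two order-specific means, at one-sided 0.025 on n−2 df.
- **SAP 6.6.1.2:** add test order to the imputation predictors and fit the same regression in each imputed data set before combining. Imputing without order and then analyzing with it would be inconsistent.
- **SAP:** carry over the period and crossover sensitivity tests from protocol 9.6, and report the number of subjects analyzed in each order.

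The order data come from the trial's own randomization, so no new data are needed. The cost is wording and one degree of freedom. With no order effect, power goes from 84.8% to 84.5% at 8:8, and to about 82% at 10:6. Changing the timing or the site stratification of the order randomization is not required; it would add little once order is in the model.

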6.6.1.2 Handling of Missing Data

In the event there are missing primary endpoint data the primary endpoint will be analyzed using a multiple imputation analysis. SAS PROC MI will be used to produce 100 imputed datasets. The imputed variable will be the difference between aided and unaided conditions at 3 months in the change in adaptive speech in noise test from preoperative. The following variables will be used as predictors in the model:

- Age
- Sex
- Pre-operative unaided adaptive speech in noise test

The estimates for the mean difference between aided and unaided change from pre-implant will be combined using PROC MIANALYZE providing an overall estimate for the primary endpoint, 95% confidence interval and one-sided p-value.

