3 SCHEDULE OF EVENTS

	Screening	Visit 1	Visit 2	Visit 3	Visit 4	Visit 5	Visit 6 EOS
Timing of Investigation	Day -1	Day -1	Day 0	Week 2	Week 4	Month 3	Month 6
Visit window (±)	NA	± 0 days	± 0 days	± 5 days	± 7 days	± 7 days	± 7 days
Time Estimation	2 hrs. 15 mins.	3 hrs. 15 mins	1 hr.	1 hr.	3 hrs.	4 hrs.	3 hrs.
Written informed consent	X						
Demographics	X						
Inclusion/Exclusion	X						
Hearing history	X						
Medical history	X						
Audiogram	X						
Concomitant Medications ¹		X	X	X	X	X	X
Sound field thresholds		X ²			X ³	X ⁴	X
Speech perception testing in quiet		X ⁵			X ⁶	X ⁷	X

¹ Collected post-Visit 1 only if changes to prescription concomitant medications associated with device or procedure-related adverse event.

² Includes sound field thresholds, unaided and aided, with Baha 5 Power on Sound Arc.

³ Visits 4 & 6 include sound field thresholds, aided, with Osia Sound Processor.

⁴ Visit 5 includes sound field thresholds, unaided and aided, with Osia Sound Processor.

⁵ Includes speech in quiet testing, unaided and aided, with Baha 5 Power on Sound Arc.

⁶ Visits 4 & 6 include speech perception in quiet, aided, with Osia Sound Processor.

⁷ Visit 5 includes speech perception in quiet, unaided and aided, with Osia Sound Processor.

	Screening	Visit 1	Visit 2	Visit 3	Visit 4	Visit 5	Visit 6 EOS
Timing of Investigation	Day -1	Day -1	Day 0	Week 2	Week 4	Month 3	Month 6
Visit window (±)	NA	± 0 days	± 0 days	± 5 days	± 7 days	± 7 days	± 7 days
Time Estimation	2 hrs. 15 mins.	3 hrs. 15 mins	1 hr.	1 hr.	3 hrs.	4 hrs.	3 hrs.
Speech perception testing in noise +5 dB SNR		X ⁸				X ⁹	
Adaptive speech in noise testing		X ¹⁰			X ¹¹	X ¹²	X
SSQ 12		X				X	
Patient Reported Questionnaire		X				X	
Device Counseling		X			X		
Surgical Follow up				X			
Fitting and Optimization of Sound Processor		X ¹³			X ¹⁴	X	X
Device Deficiencies			X	X	X	X	X
Adverse Events			X	X	X	X	X
Data Entry	X	X	X	X	X	X	X

⁸ Includes speech perception in noise, unaided and aided, with Baha 5 Power on Sound Arc.

⁹ Visit 5 includes speech perception in noise, unaided and aided, with Osia Sound Processor.

¹⁰ Includes adaptive speech in noise testing, unaided and aided, with Baha 5 Power on Sound Arc.

¹¹ Visit 4 & 6 include adaptive speech in noise testing, aided, with Osia Sound Processor.

¹² Visit 5 includes adaptive speech in noise testing, unaided and aided, with Osia Sound Processor.

¹³ Fitting with Baha 5 Power on Sound Arc.

¹⁴ Fitting with Osia Sound Processor.

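### SAP 6.6.1.2 imputes the missing 3-month difference without the Week 4 aided score; if poor early performers are lost before Month 3, the benefit would be overstated

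*SAP*

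**What the plan says.** The primary analysis (SAP 6.6.1.1) is this: "A paired t-test of superiority for the adaptive speech in noise test, comparing the aided and unaided conditions at 3-months", each condition taken as a change from the preoperative unaided score. For missing values SAP 6.6.1.2 specifies 100 PROC MI datasets. "The imputed variable will be the difference between aided and unaided conditions at 3 months", so one composite quantity is imputed. "The following variables will be used as predictors in the model": age, sex and the preoperative unaided score. No score taken after surgery is listed.

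The protocol collects such scores. In addition to the aided and unaided tests at Month 3, footnote 11 of the Schedule of Events (Protocol 3) reads: "Visit 4 & 6 include adaptive speech in noise testing, aided, with Osia Sound Processor". Visits 4 and 6 are Week 4 and Month 6.

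Protocol 9.4 says that the calculations "include allowance for attrition of up to 20" per cent, which is 4 of 20 subjects. Protocol 7.2.6 says that treated subjects who withdraw are not replaced. It also foresees withdrawal for device safety or performance problems, with only adverse-event follow-up afterwards. The sensitivity analyses in Protocol 9.6 cover period and crossover effects; neither document plans one for missing data.

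SAP 6.6.1.1 also refers to subjects with complete data, which sits awkwardly beside the imputation rule. That is a separate point.

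**The concern.** The endpoint has an unaided and an aided half. The preoperative unaided score predicts the unaided half. Nothing in the model directly measures how a subject hears with the implant, although the Week 4 aided score, on the same test and device, is in the database for anyone lost between Week 4 and Month 3.

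The imputation is unbiased only if, given age, sex and preoperative score, being missing is unrelated to aided performance. If subjects with poor early aided results were lost more often, they would be imputed as average users and the mean benefit would be too large. The study is meant to support reimbursement (Protocol 4.2), so the size of the benefit matters as well as the p-value.

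A second weakness needs no assumption about dropout. If only one of the two Month 3 tests is missing, imputing the difference as a single variable discards the half that was observed.

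**Working it through.** **1. The plan's own figure.** Inputs from SAP 5: N = 20, mean 12, SD 15, one-sided alpha 0.025, attrition up to 20%. Evaluable n = 20 × 0.80 = 16. Noncentrality = (12/15) × √16 = 3.2. Paired-t power = 84.8%, so the SAP's figure of more than 80% reproduces if 12 and 15 are the mean and SD of the paired difference. Protocol 9.4 claims "greater than 95% power under a conservatively assumed mean of 12 and standard deviation of 15" on the same inputs. That does not reproduce (92.4% even with all 20), but it is a separate matter. What carries forward is 4 missing of 20, benefit 12, SD 15.

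**2. What is imputed.** Let P be preoperative unaided, U3 and A3 the Month 3 unaided and aided scores, and W the Week 4 aided score. Then (A3 − P) − (U3 − P) = A3 − U3, so P cancels from the estimand. The alternative hypothesis makes lower scores better; write benefit B = U3 − A3.

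**3. Assumptions not in the documents.** SD of unaided scores 13; SD of aided scores 10; P–U3 correlation 0.80 to 0.90; W–A3 correlation 0.60 to 0.85. With an SD of 15 for the difference, 13² + 10² − 2ρ(13)(10) = 15², so the aided–unaided correlation is ρ = 44/260 = 0.17.

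Correlation of P with B:
- at 0.80: (10.4 − 1.7)/15 = 0.58, R² 0.34
- at 0.90: (11.7 − 1.7)/15 = 0.67, R² 0.45

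Adding W raises R² to 0.46–0.74. Keeping an observed U3 as well raises it to 0.72–0.88. The correlation of W with B is, in size, (6.0 − 2.2)/15 = 0.25 to (8.5 − 2.2)/15 = 0.42.

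**4. Simulation on those assumptions.** Regression imputation (the expectation over many imputations), with age and sex taken as uninformative. Dependence is the log-odds of leaving per SD of poorer Week 4 score. The true benefit is 12.

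| Dependence | Mean benefit, P only | With W added |
|---|---|---|
| 0 | 11.9–12.1 | about 12.0 |
| 0.5 | 12.5–12.9 | about 12.0 |
| 1 | 13.0–13.5 | about 12.0 |
| 3 (odds ratio about 20) | 13.6–14.5 | about 12.0 |
| exactly the four worst lost | 13.7–14.7 | about 12.0 |

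Moderate dependence (0.5 to 1) therefore adds 0.5 to 1.5 points (0.5/12 = 4% to 1.5/12 = 13%). Near-deterministic loss adds 1.6 to 2.5. Adding W changed the SD of the estimate by about −5% to +6%.

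**5. Second simulation.** Normal-model multiple imputation pooled by Rubin's rules, with 20 imputations instead of 100. P–benefit correlation 0.3; Week 4–benefit correlation 0.3, 0.5, 0.7 and 0.9.

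| Loss of 4 of 20 | Bias, SAP predictors | Bias, W added |
|---|---|---|
| Random, or by P only | about 0 | about 0 |
| Poor Week 4 more likely | +0.4 to +1.5 | about 0 |
| Four lowest at Week 4 | +1.4, +2.0, +3.4, +4.0 | within about 0.25 of 0 |
| Four lowest on unseen Month 3 benefit | +4.6 to +4.8 | +4.5, +3.8, +3.1, +1.4 |

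The values +3.4 and +4.0 need correlations of 0.7 and 0.9, well above the 0.25–0.42 implied in step 3, so they are extremes.

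On the test: at a benefit of 12 both models reject in most trials. With poor Week 4 performers more likely to leave, the rates are 82–86% (SAP predictors) and 76–90% (W added). With the four lowest lost they are 88–99% and 65–85%. With no true benefit and the four lowest lost (correlations 0.5 to 0.9), the SAP model rejects in 7–22% of trials against a nominal 2.5%; with W added, 1.5–3.2%.

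**6. Month 6.** A subject who withdraws before Month 3 for device problems has no later hearing test (Protocol 7.2.6). An analysis after Visit 5 (Protocol 7.1 and 9.10) may also precede Month 6. That score helps only a subject who missed Visit 5 alone and has since been tested.

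**The case against.** The strongest objection is that nothing in the documents says poor performers leave. The 20% is a planning allowance, Protocol 9.1 aims for near-complete follow-up, and Protocol 7.2.6 lists many withdrawal reasons unrelated to hearing. This stands, and the point must stay conditional. A reader might infer that the plan inflates the benefit. The documents do not support that: with loss unrelated to aided performance given the preoperative score there is no bias, and loss of good performers would understate the benefit. On the other side, Protocol 7.2.6 does foresee withdrawal over device performance, so outcome-related loss cannot be dismissed.

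A reader might also infer an overstatement of 14–20% whenever poor performers are merely more likely to leave. That size needs almost exactly the worst Week 4 performers to go; moderate dependence gives roughly 4–13%.

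The value of Week 4 is itself assumed. It is the fitting visit and is tested aided only, so its correlation with Month 3 is unknown. The preoperative score already carries information on the unaided half. Nor does Week 4 cure loss driven by the unseen Month 3 result. All of this stands; it limits the expected gain and is why a sensitivity analysis is needed as well. It does not justify leaving out the only same-device score available for a subject lost between Week 4 and Month 3.

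**Conclusion.** The concern holds in conditional form. The imputation model omits a relevant score that the trial collects, and imputing the difference as one variable discards an observed half. If loss before Month 3 tracks poor Week 4 performance, the benefit is overstated by about 0.5 to 1.5 points on the assumed 12 for moderate dependence, and by about 1.6 to 2.5 only when loss is near-deterministic. These figures assume 4 of 20 missing and the SDs and correlations in step 3 of the working, none of which the documents give.

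The exposure is mainly in the estimate and its confidence interval. The higher false-positive rates arise only when there is no true benefit and the worst Week 4 performers are lost. Month 6 is not a general remedy. This is an inexpensive improvement to the plan; the documents do not show that the result will be biased.

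**What to change.** In SAP 6.6.1.2:

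- Impute the 3-month aided and 3-month unaided scores as two variables and form the difference afterwards, so that an observed half is kept.
- Use the preoperative unaided score and the Week 4 aided score as predictors. If the model is too large for about 16 complete cases, drop age or sex first.
- Use the Month 6 aided score only for subjects who missed Visit 5 alone and whose Month 6 score is available at analysis.
- Add a delta-adjusted or tipping-point sensitivity analysis that worsens the imputed benefits step by step and reports where the one-sided 0.025 conclusion is lost.

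The cost is one SAP paragraph, a changed PROC MI call and one added sensitivity analysis, with no new data. The downside is one more predictor in a small sample: the SD of the estimate changed by about −5% to +6% when Week 4 was added to a single-variable imputation. The two-variable model was not simulated, so its precision should be checked before the SAP is finalised.
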